Forty patients with hyperlipidemia, overweight/obesity and/or HTN received FITT counseling in addition to standard care counseling by physicians during their visit in the Preventive Cardiology Clinic. Subjects were divided into "compliant" and "non-compliant" groups on the basis of information gleaned from their follow up clinic visit notes. Those that were compliant showed improvement in their lipid profile, BMI and physical activity levels. In contrast, non-compliant patients either showed no change or worsened cardiovascular risk factors. We concluded that when children with cardiovascular risk factors adhere to an exercise prescription, improvements are often achieved, and successful weight loss is sometimes realized. Unfortunately, poor compliance with exercise prescriptions was again common, and limited the effectiveness of this therapeutic intervention.

4. Design and Methods

a. Study Design

A randomized controlled pilot study comparing exercise prescription based on the FITT principle combined with BodyMedia, an online supported accelerometer, to a control group receiving physician counseling alone (standard of care). All participants will wear an accelerometer to measure physical activity for one week at the start of the intervention. At the end of that week, patients who have worn the accelerometer for more than 8 hours per day for at least 3 days will be randomly assigned to either FITT

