counseling by a pediatric exercise physiologist + interactive accelerometer, or office provider counseling (standard of care). The intervention group will be asked to continue to wear the accelerometer everyday (most waking hours) and log their activity by regularly (3 times a week) uploading the device for a period of 3 months, use of the internet must be supervised by a parent or guardian. Their activity will be monitored via the online site on a regular basis by study personnel and feedback will be provided at least once a week through email and/or phone calls. At the end of the intervention all participants will be asked to again wear the accelerometer for 1 week to assess physical activity, and complete questionnaires assessing attitudes towards and self-efficacy around physical activity. Lipid levels and blood pressures, when obtained for clinical visits in Preventive Cardiology Clinic, will be evaluated for change over the course of the intervention. Participants will be given a non-invasive pulse wave velocity test. Pulse wave velocity testing is a painless non-invasive test to evaluate the time it takes for blood to move from the heart to the rest of the body. In practice, this involves using a fingertip probe placed lightly on the brachial artery – the internal aspect of the elbow, the carotid artery – side of the neck, and the femoral artery – groin area. This final measurement is easily performed through light clothing. In order to coordinate the timing of the pulse wave, four EKG electrodes are placed on the patient. The entire procedure takes about 15 minutes in experienced hands. There is no risk involved in this non-invasive procedure. It is less painful than a blood pressure measurement. The research study will require 2 visits to the Preventive Cardiology Clinic in Boston or Waltham, based on their preference. Each visit may take up to 1-1.5 hours.

b. Patient Selection and Inclusion/Exclusion Criteria

A sample of 60 patients at increased risk for atherosclerosis will be recruited from Preventive Cardiology.

Inclusion criteria:

Subjects will be eligible for enrollment based on the following criteria:

- 1) Patients at increased risk of atherosclerosis based on lipid profiles (TC > 199 mg/dL, HDL < 40 mg/dL, LDL > 129 mg/dL, blood pressure (SBP or DBP > 90th percentile), obesity (>85%BMI)
- 2) Ages 13-21 years
- 3) Reporting an average of less than 60 minutes per day of moderate to vigorous exercise most (5) days of the week.

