- 4) Regular access to the internet with the capacity to download the device
- 5) Commitment on the part of a parent to supervise internet access as part of this protocol

Exclusion criteria:

- 1) Unable to exercise based on physician recommendations or medical conditions
- 2) Unable/unwilling to complete requirements of the research study including consent and assent.
- 3) Not proficient in English

c. Recruitment Methods

- i. HOW, WHERE and WHEN will potential subjects be recruited?

Patients will be screened for potential participation based on previous Preventive Cardiology clinic visit notes. If the child appears to meet the eligibility criteria for the study, a recruitment letter and opt-out postcard will be sent with a pre-clinic mailing at least 2 weeks prior to the scheduled visit. If patients indicate non-participation preference by returning the postcard, they will not be contacted about the study. If the postcard is not returned, study personnel will approach the patient during their clinic visit to discuss participation, eligibility and exercise habits. In addition, we will approach patients in the Lipid Clinic in Boston and Waltham that did not receive a mailing, but are potentially eligible for the study. If eligible we will obtain consent for enrollment into the study. A study visit will be scheduled during the initial clinic visit. The research study will require 2 visits to the Preventive Cardiology Clinic in Boston

or Waltham, based on participate preference. Each visit may take up to 1.5 hours. A gift card or cash incentive of \$15.00 will be given to the patient when they qualify and arrive at their first study visit. If patient requires more time to think about the study and request a phone call follow up, a study staff member will contact them via phone to discuss study participation. Phone calls will only be made if the patient has requested to be contacted at a later time and expressed interest in the study. If potential participant decides they would like to enroll in the study, verbal consent will be obtained and the device will be mailed to patient. Written consent will be obtained during the first study visit. Patients that are not interested in the study at the time of their clinic visit will be tracked in a spreadsheet and will not be contacted again.

- ii. WHAT recruitment methods and materials (e.g. posters, fliers) will be used? - *attach all materials*

Methods of recruitment will include letters and a brochure.

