Arterial Stiffness: Pulse wave velocity is a measure of the speed of transit of the pulse generally measured from the carotid to the femoral artery using ECG gated measurements of the peak pulse impulse. NIHem Hemodynamic Acquisition system quantifies pulse wave velocity (PWV), as well as other measures of arterial hemodynamics. Carotid- femoral pulse wave velocity has emerged as the "gold standard" index of aortic stiffness. The NIHem system has been previously validated to resolve pulse wave analysis in time or frequency domains and has been used extensively in the NIH/ NHLBI's Framingham Heart Study to at more than 12,000 participant visits with 90% reproducibility. Median time to complete a full set of measurements is roughly 15 minutes.

Questionnaires: A pre and post exercise questionnaire, adapted from the Youth Risk Behavior Survey and from the Trial of Activity for Adolescent Girls (Dishman 2009) will be administered. Questions will assess self efficacy, social support, perceived barriers and enjoyment related to exercise.

Laboratory testing: All study subjects will undergo testing including a fasting lipid profile consisting of TC, HDL, low-density lipoprotein (LDL), and triglycerides (TG) concentrations. Additional labs that will be collected, if available, include liver transaminase alanine aminotransferase (ALT), C-reactive protein (CRP), a relatively stable measure of the inflammatory state known to be associated with cardiovascular risk in adults, glycosylated hemoglobin (Hgn A1C) to assess long term glucose homeostasis. Fasting insulin and glucose will also be collected, if performed for clinical reasons by Preventive Cardiology or the patient's primary care.

Height, Weight, and Blood Pressure measurements will be obtained according to clinical practice guidelines. Blood pressure will be measured in a standardized manner in the right arm after 5 minutes of quiet sitting by automatic blood pressure device. One measurement of height (nearest 0.1 cm) and weight (nearest 0.1 kg) will be obtained. Body mass index (calculated as weight/height^2 [kg/m²]) using CHB EMR/PowerChart) will be used to estimate excess overall adiposity. Additional measures of auscultative blood pressure will be collected if available. [name] will interpret the anthropometric data.

f. Data Collection Methods, Assessments and Schedule (what assessments performed, how often)

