Patients enrolled in the study will be informed that the research data collection will add about an hour to their current clinical visit. However, patients will gain information about their exercise capacity.

Table 1 Data Collection Schedule

Measures	Baseline visit	12-week visit	Minutes
Height, weight, blood pressure	X	X	10
Arterial Stiffness	X	X	20
Fasting lipids, glucose, insulin, HgnA1C, CRP, ALT	X	X	20
Accelerometry	X	X	10
Questionnaires	X	X	20
Chart Review for Medical History	X	X	20
Study Total			100

g. Study Timeline (as applicable)

See Table 2. Study recruitment will start in April of 2011 and continue until target enrollment is reached or funding is exhausted.

Table 2 Study Timeline (2011)

Study Event	Mar	Apr	May	Jun	Jul	Aug	Sep	Oct	Nov	Dec	Jan	Feb	Mar
Recruitment		X	X	X	X	X	X	X	X	X			
Consent/ Baseline		X	X	X	X	X	X	X	X	X			
Patient Follow-up		X	X	X	X	X	X	X	X	X			
12-Week Assessment					X	X	X	X	X	X	X	X	X

h. Adverse Event Criteria and Reporting Procedures

Adverse events are not anticipated as part of this intervention based on the nature of the activity involved. Serious events requiring medical attention will be reported immediately to Drs. [name] and [name] as well as to CCI per the reporting policy.

- i. If the Investigator is the Sponsor/Assignee (IND or IDE-holder), he/she is responsible for selecting a qualified monitor who will monitor the progress of all clinical investigations conducted under the IND or IDE. Please describe the monitoring plan for this protocol below:**

↳ Note: the EQuIP office provides monitoring services and advice. For info, contact EQuIP @ [name].

Not applicable

5. Data Management and Statistical Analysis

Data Management Methods

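### Randomisation is set at the end of the wear week, so on at least one recruitment route the baseline questionnaire and pulse wave velocity can be taken after the arm is known

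*Combined protocol and SAP*

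**What the plan says.** **Time of randomisation.** Section 4.a has every participant wear the accelerometer for one week. It fixes randomisation at the close of that week, under this rule: "patients who have worn the accelerometer for more than 8 hours per day for at least 3 days will be randomly assigned".

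**Visits.** Section 4.a also says: "The research study will require 2 visits to the Preventive Cardiology Clinic in Boston or Waltham". Table 1 in section 4.f names them as baseline and 12-week. It places height, weight, blood pressure, arterial stiffness and questionnaires at both.

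**How patients reach the first visit.** Section 4.c separates that visit from the recruitment encounter: "A study visit will be scheduled during the initial clinic visit". The incentive is "given to the patient when they qualify and arrive at their first study visit", and section 7 ties it to the same two conditions. For patients who ask for a follow-up call and then agree to join, "verbal consent will be obtained and the device will be mailed to patient. Written consent will be obtained during the first study visit".

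**Contrary wording.** Section 4.f says that research data collection lengthens the patient's current clinical visit by about an hour, which does not fit a separately scheduled study visit.

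**Outcomes and analysis.** On the questionnaire, section 4.e says: "Questions will assess self efficacy, social support, perceived barriers and enjoyment related to exercise". Self-efficacy and arterial stiffness are named in the secondary hypotheses of section 1. Section 5.c compares change in energy expenditure between arms by a two-sample t-test, or the Wilcoxon test if the data are non-normal, and treats secondary outcomes in the same way.

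**The concern.** A change score compares the arms fairly only if its baseline could not have been influenced by allocation. Participants cannot be masked here: one arm keeps an armband for three months and receives an exercise prescription, and the other does not. A teenager who has just learned the arm may answer questions on confidence, barriers and enjoyment differently. Pulse wave velocity is less exposed, but no masking of assessors is described, and an exercise physiologist appears both as counsellor (4.a) and among the data collectors (5, Data Management Methods).

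No section requires the baseline measures to be finished before allocation is generated or disclosed. If they are taken afterwards, the self-efficacy comparison loses its pre-treatment reference. A patient randomised when the week ends who never attends the visit would have no study-visit baseline at all. On the phone route, the same order also puts randomisation ahead of written consent.

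**Working it through.** **1. Order of events by route**

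| Route | What is stated | Implied order |
|---|---|---|
| Phone follow-up (4.c) | Device mailed after verbal consent; written consent at first study visit | Wear week, randomisation (4.a), baseline visit |
| Consented in clinic (4.c) | Study visit scheduled separately; incentive on qualifying and arriving; device hand-over not stated | Probably the same, but inferred |
| Section 4.f sentence | Data collection added to the current clinical visit | Baseline measures could come before the wear week |

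The third reading would give clean baselines. It would also leave no study visit between randomisation and week 12 for the intervention arm's FITT session, and neither 4.a nor 4.d says where or when that session is held. Sections 4.a, 4.c and 4.f therefore need reconciling on any reading.

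**2. The plan's own sample size**

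Inputs from 5.c and 5.d: 20 per arm evaluable, difference 0.9 SD, two-sided 0.05. The plan says only that power is adequate, so 80% is an assumption.

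- n per arm = 2(1.960 + 0.842)² / 0.9² = 19.4, rounded up to 20.
- Power with 20 per arm: 81.2% (normal approximation), 79.2% (exact t).
- Attrition: 20 / (1 − 0.30) = 28.6, so 29 per arm against 30 planned; 30 × 0.70 = 21 completers.

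These figures reproduce, and this point changes none of them.

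**3. What a post-allocation baseline does to a change score**

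Let δ be the true effect, and b the amount by which knowing the arm raises the baseline difference (intervention minus control) without carrying over to week 12. Then the expected difference in change is δ − b. With equal SDs at both times and an assumed correlation of 0.5, the variance of change is 2σ²(1 − 0.5) = σ², so b is in the same SD units as the change.

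Both plausible reactions give b > 0 for self-efficacy: enthusiasm raises the intervention baseline, and disappointment lowers the control baseline.

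**4. Illustration, 20 per arm**

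T-test with 38 degrees of freedom, critical value 2.024, non-centrality (δ − b)√(20/2). The values of b are assumptions; the documents give none.

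| b (SD) | No true effect: any p<0.05 | of which favours intervention | of which favours control | True 0.9 SD appears as | Power for it |
|---|---|---|---|---|---|
| 0 | 5.0% | 2.5% | 2.5% | 0.9 | 79% |
| 0.2 | 9.5% | 0.5% | 9.0% | 0.7 | 58% |
| 0.3 | 15.2% | 0.2% | 15.0% | 0.6 | 46% |
| 0.5 | 33.8% | 0.02% | 33.8% | 0.4 | 23% |

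Almost all the extra rejections favour control. The practical loss is a hidden benefit.

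**The case against.** The strongest reply is that this is a gap in wording, not an established error of sequence.

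- The device demonstrably precedes the first study visit only on the phone route. Qualifying, in 4.c, is undefined and might mean meeting the inclusion criteria. The accelerometry entry under the baseline visit in Table 1 could be either fitting or download. **This stands:** a reader might infer that every patient is randomised before the baseline visit, and the documents do not establish that.
- Since written consent is taken at the first study visit on the phone route, staff might naturally allocate there, leaving only the order within the visit open. Section 4.e also describes the questionnaire as given before and after exercise. **This stands in part:** both suggest a sensible intention, but the only stated randomisation point is the end of the wear week, and nothing puts the baseline measures before disclosure.
- A reader might infer that patients are already counselled before their baselines. That is conjecture, because the timing of counselling is not given.
- Blood pressure is a weak example. The background summary and 4.a also draw it from clinical encounters, which may pre-date randomisation, and 4.e uses an automatic device. **This stands.** Pulse wave velocity is intermediate: 4.e cites 90% reproducibility for the system, and no clear direction of bias can be given.
- A reader might take the inflated rejection rates as a risk of falsely favouring the intervention. The split by direction shows the reverse for self-efficacy, and nothing in the documents supports any particular shift.
- Section 5.c plans no routine baseline adjustment, only regression for suspected confounding, so adjusting for a post-randomisation baseline is a possibility and not a planned step.

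**Conclusion.** The concern holds in limited form. On the mailed-device route, following 4.a and 4.c literally allocates patients before the baseline questionnaire and pulse wave velocity are taken. The same is probable, but unstated, for patients consented in clinic. Self-efficacy is the outcome most exposed, and the likely bias runs against the intervention. Its size is unknown; the tabulated shifts show only how a given shift would carry through, and they rest on a correlation of 0.5 and no carry-over to week 12.

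It would be wrong to infer that the primary comparison is compromised. Baseline energy expenditure comes from the wear week, which precedes randomisation. This is a change that should be made for the sake of named secondary outcomes; it is not a threat to the main result of the pilot.

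**What to change.** In section 4.a, replace the randomisation sentence with an explicit sequence, for example: *Patients who meet the wear rule attend the first study visit. Written consent is confirmed and all Table 1 baseline measures are completed. Randomisation then takes place and the arm is disclosed. FITT counselling follows for the intervention arm.*

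Add a randomisation row to Table 1 after the baseline measures. Bring sections 4.c and 4.f into line: state when the device is given to patients consented in clinic, what qualifying means, and whether the baseline visit is the clinical visit or a separate one.

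The cost is protocol wording. No visit, staff or procedure is added, and the device can be downloaded at the same visit to check the wear rule. The small downside is that allocation waits until the visit. In return, patients who never attend are not randomised, and written consent comes before allocation.

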- Our primary hypothesis is that this interactive technology coupled with support from a exercise specialist will increase the energy expenditure of our patients over standard of care provider counseling
- Secondary hypotheses include greater improvement in measured physical fitness, lipid profiles, blood pressure, arterial stiffness, BMI, BMI percentile, and self-efficacy in the intervention group compared to control.

2. Background and Significance

Obesity is increasingly common in childhood and adolescence, and is a major threat to health. Obese pediatric patients have high rates of abnormal cholesterol and high blood pressure (AHA 2010) and childhood obesity is predictive of type 2 diabetes and cardiovascular disease (CVD) (Morrison 2008). Studies suggest that regular physical activity can reduce cardiovascular risk factors in children. Exercise training can improve cardiovascular risk factors (Ferguson 1999) and the intra-individual clustering of cardiometabolic risk factors (Reinehr 2009), in individuals with obesity (Klijn 2007) and diabetes (Caranti 2007). Reduction in risk factors may occur both by direct effects (e.g. blood pressure reduction, increasing HDL), and indirectly through weight reduction. National guidelines recommend that children accumulate at least 60 minutes per day of moderate to vigorous physical activity on most days of the week (CDC 2010), based on evidence of physiologic benefits (Strong 2005). However, most children are not meeting these recommendations; declining levels of physical fitness among children and adolescents contribute to the obesity-associated health risks of future generations (American Heart Association, 2005).

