Data will be collected by study personnel including exercise physiologist, research fellow, head EKG technician and exercise student intern. The research team will assure that all data is collected. The data will be recorded in a de-identified manner using study IDs only. The key between participants and study IDs will be stored in a password protected electronic file. The data will be entered using a standard data management program (REDCap) on an ongoing basis. The data will be examined systematically for quality control and data cleaning purposes during the course of the study and again at the end. A portion of the data forms will be double entered for quality assurance purposes. The assistance of the Clinical Research Program will be solicited for technical support in these areas.

b. Quality Control Method The data will be examined systematically for quality control and data cleaning purposes quarterly during the course of the study and again at the study end prior to analysis.

c. Data Analysis Plan

The primary test of hypothesis is the comparison of change in Energy Expenditure (ΔEE) between baseline and final visit (12 weeks) in children receiving FITT Counseling plus BodyMedia as compared to children receiving physician counseling alone (standard of care/control). A two sample t-test will be used for this comparison. In the event of non-normality, the Wilcoxon rank sum test will be used. Secondary outcomes will be analyzed similarly. Linear regression will be used to adjust for any suspected confounding. In all tests, a two tailed p-value <0.05 will be considered statistically significant.

d. Study sample size and power considerations. . A total sample size of 40 (20/group) would provide adequate power to detect differences in physical activity counts as small as 0.9 standard deviations. Based on previous studies and clinical experience we expect $\leq 30\%$ attrition rate over 6 months: 30 patients per study group will be enrolled to ensure ≥ 20 per group complete the study

e. Study Organization

The study group will meet monthly to review progress and results of the study. Dr. [name] and [name] will review testing results as they are received. The Clinical Research Team will oversee recruitment and study activities for the Study.

f. Data and Safety Monitoring Plan

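### BMI change is compared across participants with and without raised BMI, with no pre-specified use of baseline weight status; name it as a covariate and report BMI change by weight status

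*Combined protocol and SAP*

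**What the plan says.** **Eligibility.** Inclusion 1 in section 4.b gives cholesterol limits followed by "blood pressure (SBP or DBP > 90th percentile), obesity (>85%BMI". The items are separated by commas, and no other criterion requires a raised BMI. Two other places support reading them as alternatives. Section 3 describes the clinic's earlier cohort as "Forty patients with hyperlipidemia, overweight/obesity and/or HTN received FITT counseling". Section 4.c adds that "we will approach patients in the Lipid Clinic in Boston and Waltham that did not receive a mailing".

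**Outcome.** Section 1 states that "Secondary hypotheses include greater improvement in measured physical fitness, lipid profiles, blood pressure, arterial stiffness, BMI, BMI percentile, and self-efficacy" are expected in the intervention group. Section 4.e says that BMI "will be used to estimate excess overall adiposity". The direction of improvement is not defined by baseline weight status.

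**Analysis.** Section 5.c tests change in energy expenditure with a two-sample t-test (Wilcoxon if non-normal) and then says "Secondary outcomes will be analyzed similarly". It allows linear regression where confounding is suspected but names no covariate. No restriction, subgroup or breakdown by weight status is given.

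**Allocation.** Section 4.a says that participants "will be randomly assigned to either FITT" counselling with the device or standard counselling. It names no stratification factor and describes no randomisation method.

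**The concern.** BMI is collected as a measure of excess adiposity, but the comparison includes participants who may have none. Two things follow. If normal-weight participants do not change, they pull the arm difference towards zero, and a null result is hard to interpret. If their BMI does fall, the test credits the fall to the intervention as improvement, although for them it need not be a benefit. The second case is not remote, since section 4.d describes the device as a weight management system with a food log that may aid weight loss.

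Baseline weight status may also predict change in outcomes related to body size. With about 20 completers per arm, leaving it out of the model can waste precision. Choosing covariates only once confounding is suspected leaves the model open until the data have been seen.

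**Working it through.** **1. The plan's own figure (section 5.d).** Inputs: 0.9 SD, two-sided 0.05, 20 per group. The plan calls the power adequate without a number, so 80% is assumed.
- n = 2(1.96 + 0.84)²/0.9² = 19.4, so 20 per group. The exact t-test has 79.2% power at 20 and needs 21 for 80%.
- Attrition of 30%: 20/0.7 = 28.6, so 29 per group against 30 planned.

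The figure reproduces, but it is for physical activity counts, not BMI.

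**2. Dilution (illustration only).** Let s be the overweight share, 0.9 SD the BMI effect in overweight participants (borrowed from section 5.d) and e the effect in the others. The whole-sample effect is d = 0.9s + e(1 − s). The restricted test keeps 0.9 SD but has only 20s per arm. Exact t-test power, 20 completers per arm:

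| s | Whole sample, e = 0 | Whole sample, e = 0.45 | Overweight only |
|---|---|---|---|
| 1/3 | d = 0.30, 15% | d = 0.60, 46% | 32% |
| 1/2 | d = 0.45, 28% | d = 0.675, 55% | 48% |
| 2/3 | d = 0.60, 46% | d = 0.75, 64% | 61% |

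With e = 0.9 the whole sample has 79%. The restricted test is stronger at e = 0 and weaker at half the effect. Equating the two noncentralities gives the approximate break-even: 0.9s + e(1 − s) = 0.9√s, so e = 0.9√s/(1 + √s). That is 0.33, 0.37 and 0.40 SD for the three shares. The documents give neither s nor e.

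**3. Chance imbalance without stratification.** With X₁ and X₂ independent binomial(n, p), the probability that |X₁ − X₂| ≥ 0.2n is:

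| Per arm | p = 30% | p = 50% |
|---|---|---|
| 30 (gap of 6 or more) | 12.0% | 15.5% |
| 20 (gap of 4 or more) | 22.6% | 26.8% |

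Fixing the overweight total gives unstable figures. At 20 of 40 the probability is 34.3%, but at 19 or 21 of 40 it is 20.5%. At 30 of 60 it is 19.6%, but at 29 or 31 it is 12.0%. With equal arms the count difference can take only even or only odd values, so an even total puts the cutoff exactly on an attainable value. The binomial figures are the fair summary.

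**4. What imbalance does to the test.** Assume 20 per arm, half overweight, and weight status shifting the outcome by 1 SD.
- Simulated type I error of the unadjusted test is 0.05, so validity is intact.
- Weight status adds variance 1² × 0.5 × 0.5 = 0.25, so the SD is √1.25 = 1.118. A 0.9 effect becomes 0.9/1.118 = 0.805 SD, and simulated power is about 70%.
- With weight status as a covariate, simulated power is about 78%.
- If weight status predicted nothing, the unadjusted test would have 79% and the adjusted test about 78%. The most that is lost is about one percentage point.

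**The case against.** The strongest defence is that the plan tests an average effect in a mixed-risk clinic population, which is an ordinary target. The same mixture exists for lipids and blood pressure, since an obese participant may have normal values. BMI is one of several secondary outcomes in a pilot, and neither the primary test nor the sample size depends on it. All of this stands, and it limits the severity.

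A reader might infer three stronger things that the documents do not support.
- *The BMI test should be confined to overweight participants.* That is a trade-off. It gains power only if the effect in normal-weight participants is well below that in the others (under about 0.33-0.40 SD in the illustration). At half the effect the whole sample does better for every share shown. It would also set aside randomised participants and leave roughly 7 to 13 per arm.
- *Unstratified allocation biases the comparison or makes it unreadable.* Under randomisation the standard error already allows for chance imbalance. Nor does imbalance cause the dilution, and stratifying would not remove it.
- *The sponsor chose to ignore weight status in allocation.* The protocol is silent on the randomisation method, and silence is not a decision.

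The regression clause in section 5.c would permit adjustment for baseline BMI. As it names no covariate, it does not commit the analyst to it.

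**Conclusion.** The concern holds in limited form, and its severity is minor. On the natural reading of inclusion 1, the BMI comparison mixes participants with and without excess adiposity. The plan has no pre-specified way to separate a diluted effect from a small one, or to keep BMI falls in normal-weight participants from being read as benefit. The all-participant mean difference remains a valid and interpretable average.

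The size of the dilution is unknown, and the subset power figures are illustrative only. The imbalance probabilities assume an overweight share of 30-50%. The gain from adjustment (about 70% to 78% power) assumes a 1 SD prognostic effect of weight status, which the documents do not give. No passage links weight status to change in energy expenditure, so for the primary outcome the case for the covariate is possible precision at almost no cost, not a demonstrated flaw. The eligibility reading is itself an inference. If a raised BMI was meant to be required, the dilution point falls away and the criterion needs rewording.

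**What to change.** 1. **Section 5.c, covariate.** Pre-specify a linear model for change with treatment arm and baseline BMI (or BMI >85% yes/no) for the primary energy expenditure comparison and the secondary BMI outcomes. This replaces adjustment for confounding suspected afterwards. Say how this model relates to the Wilcoxon fallback, which carries no covariate.
2. **Section 5.c, reporting.** Keep all randomised participants as the main BMI analysis. Report BMI and BMI-percentile change by arm within baseline BMI >85% yes and no, with confidence intervals, as a pre-specified supportive analysis. State that a fall in the lower group is not counted as benefit. The covariate alone does not cure the dilution; this breakdown makes it visible.
3. **Section 4.b.** State the and/or logic of inclusion 1.
4. **Optional, section 4.a.** Stratify the randomisation list by BMI >85% yes/no in small blocks.

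The cost is a few sentences, one degree of freedom and, if step 4 is taken, a slightly more complex list. Height and weight are already measured at baseline (Table 1), so no visit or participant is added. The groups in step 2 will be small and their intervals wide.
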